 - For school-based research where class time is used, describe in detail the activities planned for non-subjects and explain where both subjects and non-subjects will be located during the research activities.
 - Indicate that the instruments used are in the public domain or provide appropriate documentation of permission to use each scale.
 - Use any diagrams, charts or tables necessary to make subject participation clear to readers. Attach additional pages if necessary.

Protocol Title: Assessing an HIV Education and Screening Intervention in African American Churches

Protocol Type: Expedited/Full Board Application

Date Submitted: 11/21/2017

Approval Period: 12/05/2017-12/04/2018

Important Note: This Print View may not reflect all comments and contingencies for approval. Please check the comments section of the online protocol. Questions that appear to not have been answered may not have been required for this submission. Please see the system application for more details.

- Be sure to identify what procedures are experimental and what are standard of care or established practice for the condition/situation.

Please note: Do NOT respond "See Attachment Section". If you would like to add tables, charts, etc., attach those files in the Attachment section (#16).

Determination of Number of Churches/Sample Size: Power Analysis. Sample size calculations were based on: a) change in expected self-reported HIV testing rates (primary outcome) from baseline to 12-month assessment and b) a group randomization and matched pair design based on a range of 5 to 7 paired churches (10 to 14 churches). To calculate power, we used Hayes' approach for cluster randomized trials through the specification of a coefficient of variation (CV) of cluster rates, which defines relative variation between clusters, rather than an intraclass correlation. We used our TIPS pilot study findings as the basis of our analysis (there are no other known studies on pre-post HIV testing rates with AA participants nested in churches) and expect similar HIV testing rates in the proposed study. Based on our CV estimates, we would have sufficient power with 10 to 12 churches (110 baseline participants per church; >65 participants at 12 months) to achieve 84% to 91% power, respectively, to detect this difference with a Type I error rate of 5%; these power calculations are conservative. However, we will include 14 churches to protect power against possible church attrition.

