Important Note: This Print View may not reflect all comments and contingencies for approval. Please check the comments section of the online protocol. Questions that appear to not have been answered may not have been required for this submission. Please see the system application for more details.

i) **Describe the statistical methods of the research and plans for analysis of the data (i.e. planned statistics, justification of sample size, etc.).**

Data will be initially summarized using means, standard deviations, and percentages. Our primary outcome is self-reported receipt of HIV/STD testing (tested vs. not-tested) at 12 months. We'll also examine outcomes at 6 months. Churches are the unit of randomization and participants nested in churches will be the level of analysis. Therefore, differences between intervention and standard information groups will be analyzed using random effects logistic regression to account for the clusters and the pairing, or matching, of churches. Multilevel, multivariate models will include fixed-effect terms for experimental condition and potential mediators and moderators, as well as random effect terms for church nested in treatment condition and individual nested within church. This approach has been widely used in other church-based studies. Adjusted odds ratios for HIV testing (and confidence intervals) will be computed for mediators/moderators. Other covariates will be added as indicated by univariate analyses conducted on baseline data. A propensity score matched analysis will also be run using all available covariates.

Amendment for post study focus group survey/discussion:

Survey data will be summarized using means, standard deviations, and percentages. Focus group discussions will be audio-recorded, transcribed, and coded. Coding protocols will include initial transcription "open-coding" (e.g., identifying key words, themes, behavioral descriptions), category grouping (e.g., church-based health screening barriers), and code map development to further categorize and retrieve factors (e.g., challenges, facilitators) related to delivery/receipt of programming/services and intervention refinement strategies/tools. Intercoder agreement will be assessed with the kappa coefficient.

* * * Drugs and Devices * * *

5. Drugs and Devices

Device

Will the study be registered on an online website?

Y

If yes, state which website(s):

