Only six of the eight churches that met the eligibility criteria participated in Wave 1. Palestine Missionary Baptist Church will not be participating due to other church priorities. Victorious Life Church was delayed due to other commitments and will participate in Wave 2. Therefore, Wave 2 churches will include 8 churches.

Church recruitment is ongoing for Wave 2 and additional churches will be added in subsequent amendments.

March 2016 Amendment:
Added participating churches
- Paseo Baptist Church
- Swope Parkway United Christian Church

August 2016 Amendment
~ Removed church name, El Shaddai International Ministries Church, previously listed under "March 2016 Amendment".
~ Added participating church, Good Samaritan Baptist Church

Amendment for focus groups survey/discussion: Recruitment of post study survey/focus group participants will take place in participating churches by the PI (or other research team member), who will attend participating churches' services/ministry meetings to share information about the post study focus groups. The evaluation procedures will be reviewed using an informed script/form (see Post Study Informed Consent Script/Form). Survey completion and focus group participation will be entirely voluntary.

b) Describe solicitation through the use of advertising. (Include plans for using posters, flyers, announcements, newspaper, radio, television or internet ads, face to face interactions, direct mail or phone contact, subject pools, etc.)

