Statistical Analysis Plan Cover Page

Official Study Title: Assessing HIV Screening in African American Churches
NCT02529644

Latest IRB approval date: 12/5/2017

Date created: May 7, 2013

Note: No updates were made since date created

Statistical Analysis Plan

Specific Aim 1. Test a religiously/culturally-tailored, eTPB church-based HIV screening intervention against a standard information condition and a waitlist control condition on receipt of HIV screening and HIV sexual risk behaviors among an AA church-population at 6 and 12 months. Hypothesis. The religiously/culturally-tailored, eTPB church-based HIV screening intervention will evidence higher HIV screening rates and lower sexual risk behaviors than the standard information and waitlist control conditions.

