Data will be initially summarized using means, standard deviations, and percentages. Our primary outcome is receipt of HIV testing (tested vs. not-tested) at 12 months. We'll also examine outcomes at 6 months. Churches are the unit of randomization and participants nested in churches will be the level of analysis. Therefore, differences between intervention and standard information groups will be analyzed using random effects logistic regression to account for the clusters and the pairing, or matching, of churches. Multilevel, multivariate models will include fixed-effect terms for experimental condition and potential mediators and moderators, as well as random effect terms for church nested in treatment condition and individual nested within church. This approach has been widely used in other church-based studies. Adjusted odds ratios for HIV testing (and confidence intervals) will be computed for mediators/moderators. Other covariates will be added as indicated by univariate analyses conducted on baseline data. A propensity score matched analysis will also be run using all available covariates. We will use R and SAS statistical software generalized estimating equations and generalized linear mixed modeling for data analyses to determine if there is a difference in HIV screening rates over time between intervention and standard information groups with/without adjusting for covariates. We will do a stratified analysis by Wave to explore differences between: a) Wave 1 intervention and waitlist groups and b) Wave 1 standard information and waitlist groups using similar analysis methods described above. A similar process will also be used to analyze HIV sexual risk behaviors using mixed-model ANOVA programs that allows for adjustment of participant nonindependence within churches.

Specific Aim 2. Evaluate the role of potential mediators and moderators associated with HIV screening behaviors among a church-population at 6 and 12 months.

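### Were the 84% and 91% power figures computed for unmatched churches, and does the plan leave open whether the pairs are kept?

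*Protocol*

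**What the plan says.** Protocol section 4a (power analysis) bases the sample size on "a group randomization and matched pair design based on a range of 5 to 7 paired churches (10 to 14 churches") and uses Hayes' method with a CV of cluster rates taken from the pilot. It claims "sufficient power with 10 to 12 churches (110 baseline participants per church; >65 participants at 12 months) to achieve 84% to 91% power", "to detect this difference with a Type I error rate of 5%; these power calculations are conservative". It then adds a reserve: "However, we will include 14 churches to protect power against possible church attrition".

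For the analysis, Protocol section 4i and SAP Specific Aim 1 use the same sentence. The arms are compared by "random effects logistic regression to account for the clusters and the pairing, or matching, of churches". The next sentence concerns multilevel, multivariate models that also carry mediators and moderators, and lists "random effect terms for church nested in treatment condition and individual nested within church". Neither document writes out a pair term.

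The February 2016 amendment in Protocol section 8a reports that "Only six of the eight churches that met the eligibility criteria participated in Wave 1". One church withdrew, one moved to Wave 2, and Wave 2 was set at eight churches. The SAP cover page, for a plan created in 2013, says "Note: No updates were made since date created".

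**The concern.** Hayes' formula for matched pairs charges one more church per arm than the unpaired formula at the same CV. If power was computed unpaired but described as paired, the stated 84% and 91% could be too high for the design. The reserve of 14 churches would then cover the loss of one pair at 84%, not two.

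The pairing also affects the test. In a church-level t-test with 7 pairs, keeping them leaves 6 degrees of freedom and breaking them leaves 12. The critical values are 2.447 and 2.179, so the paired interval is 12% wider at the same standard error (2.447/2.179 = 1.123). The text promises to account for pairing, yet the listed random terms contain no pair. A reader could fear that the choice would be made after the result was seen. The loss of two churches from Wave 1, with no word on their pairs, adds to that.

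**Working it through.** **Inputs.** From Protocol 4a: 84% at 10 churches (c = 5 per arm), 91% at 12 (c = 6), alpha 5%, m = 65 per church at 12 months. From the pilot study in Protocol 3a: 59% v 41% at 12 months. The protocol states neither that these are the two rates used for power, nor the CV k, nor the sidedness. All three are assumptions here.

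**Formula.** Power = Φ(d·√((c − a)/V) − z), with V = p0(1 − p0)/m + p1(1 − p1)/m + k²(p0² + p1²). Unpaired, a = 1. Paired, a = 2 and k is the within-pair CV.

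**Reproducing the stated figures, unpaired.** With k = 0.12, V = 0.00744 (within church) + 0.00743 (between church) = 0.01488.

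- c = 5: 0.18·√(4/0.01488) = 2.952; 2.952 − 1.960 = 0.992; power 84%.
- c = 6: 0.18·√(5/0.01488) = 3.300; 3.300 − 1.960 = 1.340; power 91%.
- c = 7: 0.18·√(6/0.01488) = 3.615; 3.615 − 1.960 = 1.655; power 95%.

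**Which form fits best.** If k, m and the rates are the same at both counts, they cancel. Two-sided, 84% means 0.994 + 1.960 = 2.954.

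- Unpaired: 2.954·√(5/4) = 3.303, giving 91.0% (90.7–91.4% if 84% is read as 83.5–84.5%).
- Paired: 2.954·√(4/3) = 3.411, giving 92.7% (92.3–93.0%).
- One-sided: unpaired 90.0–90.8%, paired 91.6–92.3%.

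So the unpaired form fits better. The paired form misses by 1.7 points two-sided.

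**Is the paired form excluded?** No.

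- A one-sided exact paired t-test that starts at 83.5–84.5% gives 91.2–91.9% at 12 churches, and so can round to 91%.
- The protocol speaks of CV estimates in the plural. In the two-sided paired form, 84% at 5 pairs needs a CV of 0.083–0.086 and 91% at 6 pairs needs 0.0905–0.095. A gap of about 0.004 reconciles them.
- The cluster size is given only as an inequality. With 70 per church at 10 churches and 65–66 at 12, a single paired CV near 0.092 yields both figures after rounding.

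**What the paired form gives.**

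| Within-pair CV | 10 churches | 12 churches | 14 churches |
|---|---|---|---|
| 0.12 (matching removes no variance) | 72% | 84% | 91% |
| 0.085 (about half removed: (0.085/0.12)² = 0.50) | 84% | 93% | 97% |

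**Break-even at an overall CV of 0.12.** The share of between-church variance that matching must remove for paired power to equal unpaired power is 1 − [V(c − 2)/(c − 1) − 0.00744]/0.00743. This is 50%, 40% and 33% at 10, 12 and 14 churches.

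**Effect on the test.** Church-level t-tests were simulated (14 churches, 65 per church, 59% v 41%, CV 0.12, two-sided, 200,000 trials). Paired v unpaired power is 90% v 94% if matching does nothing, and 96% v 96% if it removes half the variance. The two tests disagree on significance in about 4–6% of trials. With no true effect and half the variance removed, the unpaired test rejects in about 3% of trials rather than 5%, so breaking the pairs errs on the cautious side.

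**The case for a change.** The best case for acting does not depend on guessing the formula. Both documents promise to account for pairing but name no pair term. The SAP names both generalized estimating equations and mixed models without tying either to the primary test. The set of churches changed after the SAP was written. The 2017 renewal form says data entry was still going on and the study was not in the analysis stage, so clarification would have cost only wording. The power inputs are also unreported in the public text.

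The reporting gap is real, but its weight is limited. The sentence on the arm comparison commits to accounting for the pairing. The list of terms comes from the next sentence, on models that also carry mediators and moderators, and it need not be exhaustive. An analyst following the stated intent would include the pair. The degrees-of-freedom contrast belongs to a church-level t-test, whereas the plan is a participant-level logistic model. It also holds the standard error fixed, when reducing that error is the purpose of matching.

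Two churches leaving Wave 1 does not show that pairs were broken. They may have formed one pair, and the text does not say that pairing or randomisation had already taken place. Six churches in Wave 1 and eight in Wave 2 still make 14. The grant application listed among the protocol attachments may hold the missing power inputs.

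**Conclusion.** The concern does not call for a change. Under a single CV and cluster size, the figures fit the unpaired form best (CV about 0.12 at 59% v 41%, 65 per church, two-sided). The paired form is not excluded, and the stated power is not shown to be wrong. The least favourable paired series, 72%, 84% and 91% at 10, 12 and 14 churches, assumes that matching on size, socio-economic status and denomination removes no variance. Even then the planned 14 churches give about 91%, and losing one pair leaves 84%. A reserve that survives the loss of two pairs at 84% needs matching to remove about half of the between-church variance.

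Whether to keep or break 7 pairs is a fair trade-off between degrees of freedom and variance removed. At the CV implied by the plan's own figures, it moves power by at most about 4 points with 14 churches. The unspoken pair term is a gap that an analyst would fill from the stated intent, and the unreported CV, its type and the sidedness are missing detail. All of this rests on the pilot rates being those used for power, which the protocol implies but does not state.

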Recruitment of Churches. Seventeen KC urban churches provided letters of support to participate in the study (see Attachments) and will be approached to formally participate in the study. Eight churches have met criteria and agreed to participate in Wave 1 of the study (See their Memorandum of Agreements in Attachments). Selection criteria for churches include: a) a minimum of 150 AA church members, b) a pastor willing to assist in study delivery activities; c) ongoing outreach services (e.g., daycares, food/clothing programs, social services) to about 50 adult community members minimum, and d) not hosted and HIV-related event in the last year. To maximize church participation, all churches will receive: a) \$3,000 for assisting in study delivery and recruitment-retention activities and; b) \$1,600 for stipends for church liaisons coordinating study activities; and b) approximately \$1,200 technology upgrades (e.g., phone message system for HIV/STD testing and survey event reminders); total of approximately \$5,800. All churches will also receive promotional items (t-shirts, church fans).

Recruitment of Church/Community Participants. Impact will be tracked among 110 participants (approximately 70 church members and 40 community members) from each of 14 AA churches, for a total of 1,540 participants (N = 770 intervention and 770 standard information church participants) assessed at baseline, 6, and 12 months. Similar to our pilot study, all participants must be: a) aged 18 to 64; b) willing to participate in 3 surveys after church services or community outreach events; c) willing to provide contact information (i.e., two phone numbers, mailing/email address, phone numbers for two persons with whom they have ongoing contact; and d) regularly attend church (>once a month) or use church outreach services (e.g., daycare services, food programs) > 3-4 times/year. Participants will receive \$25 for completing baseline surveys (including \$25 for additional waitlist baseline churches), \$25 at 6-month, \$30 at 12-month assessments, and snacks for their participation time and travel in completing the Health Beliefs and Behavior surveys. Participants will complete surveys (about 20-45 minutes) immediately after church services or during church outreach ministry events. They will receive compensation immediately after completing the survey at each time point.

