At least 2 church leaders, or church health liaisons, will coordinate implementation of their church's TIPS activities. These CHLs will be trained to monitor and report their church's implementation activities monthly over the 12-month study period by responding to questions on the CHL Intervention or Comparison Church Implementation Monitoring Form (Independent on if they're in an intervention and comparison church; see Attachments). CHL's will complete implementation questions (no personal or behavioral information is requested) directly into REDCap, an online data entry database supported by UMKC's Center for Health Insights, which has been used extensively by research and community organizations around the world (see Section 11.c for further information about REDCap). CHL's at participating churches will have password access to this system to enter process data on intervention implementation information (e.g., number of persons attending events, location of events, organizations and resources assisting in implementing events, challenges and accomplishments related to the events). No personal health or behavioral data will be collected on intervention Implementation -- only program

Protocol Title: Assessing an HIV Education and Screening Intervention in African American Churches

Protocol Type: Expedited/Full Board Application

Date Submitted: 11/21/2017

Approval Period: 12/05/2017-12/04/2018

Important Note: This Print View may not reflect all comments and contingencies for approval. Please check the comments section of the online protocol. Questions that appear to not have been answered may not have been required for this submission. Please see the system application for more details.

evaluation information. The online system will significantly reduce the amount of time needed for church liaisons to provide implementation data by allowing them to select responses from a pull down menu and provide short string text for open ended responses.

Research Design: We will use a 2-arm, research design with 14 churches (7 intervention and 7 standard information control churches) matched on church membership size, SES, and denomination. Matched churches will be randomly assigned to one of two Waves and then to intervention or standard information arms within their Wave. To optimize study management, 8 churches will be in Wave 1, and 6 Wave 2 churches will be 6-month waitlisted.

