Attachment Health Beliefs and Behaviors 6 month amendment
Version 1 dated 2-2-2016

Document Name Health Beliefs and Behaviors 6 month amendment
Version 1 dated 2-2-2016

Document Type **Other Documentation**

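### Waves are described as randomised 8/6, but the protocol reports 6/8 with one church lost, one moved and others added later, so the waitlist in SAP Aim 1 is not a purely randomised control

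*Protocol*

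**What the plan says.** Protocol section 4a (Research Design) describes two-step randomisation: "Matched churches will be randomly assigned to one of two Waves and then to intervention or standard information arms within their Wave". It gives the split: "8 churches will be in Wave 1, and 6 Wave 2 churches will be 6-month waitlisted". The recruitment paragraph of the same section says: "Eight churches have met criteria and agreed to participate in Wave 1 of the study". Sections 8a and 8b repeat this, and 8b adds that more churches will join for Wave 2.

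Section 8a, under its February 2016 entry, reports what happened: "Only six of the eight churches that met the eligibility criteria participated in Wave 1". One of the other two withdrew because of competing priorities. The second was delayed by its own commitments and was placed in Wave 2, which then comprised eight churches. The entry continues: "Church recruitment is ongoing for Wave 2 and additional churches will be added in subsequent amendments". Participating churches are listed there and under the March and August 2016 entries.

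The SAP cover states that nothing has been updated since May 2013. Its Aim 1 tests TIPS against both standard information and a waitlist control at 6 and 12 months. The hypothesis is that TIPS "will evidence higher HIV screening rates and lower sexual risk behaviors than the standard information and waitlist control conditions". The analysis paragraph says: "We will do a stratified analysis by Wave to explore differences between: a) Wave 1 intervention and waitlist groups", and adds the matching contrast of Wave 1 standard information against waitlist.

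**The concern.** If Waves had been randomised and kept, the waitlisted churches during their waiting period would be a legitimate control for Wave 1. Section 8a shows that final Wave membership was not the product of randomisation alone. A church that postpones for its own reasons, or that joins later, may differ from one that was ready at the start in leadership support, outreach activity or baseline testing. Where the waiting period falls in a different calendar interval, background change in HIV testing is added to that.

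Both SAP waitlist contrasts carry this confounding. At stake is whether a difference between Wave 1 TIPS churches and waitlist churches could be reported, under a prespecified hypothesis, as an effect of TIPS. As worded, Aim 1 gives the waitlist the same standing as the standard information control.

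**Working it through.** **The plan's own figure.** The only computed design figure is the power in section 4a for TIPS versus standard information: 84% with 10 churches and 91% with 12. No power is given for any waitlist contrast. The coefficient of variation k between churches is not reported, so strict reproduction is impossible. The Hayes unmatched form is

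power = Φ(√[(c − 1)(p1 − p0)²/V] − 1.96), with V = [p0(1 − p0) + p1(1 − p1)]/m + k²(p0² + p1²).

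Inputs are p1 = 0.59 and p0 = 0.41 (pilot 12-month rates, section 3), m = 65 and two-sided 5% (assumed). With k = 0.12, V = 0.4838/65 + 0.0144 × 0.5162 = 0.01488. Power is then 83.9% for c = 5 per arm and 91.0% for c = 6. The matched form (c − 2) fits less closely: 83.0% and 92.0% at k = 0.088. The stated figures are plausible, and the present point does not depend on them.

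**Step 1: church counts.**

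| | Section 4a (plan) | Section 8a (reported) |
|---|---|---|
| Wave 1 | 8 | 6 |
| Wave 2 | 6 | 8 |
| Total | 14 | 14 |

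Two of the eight churches intended for Wave 1 (2/8 = 25%) were not in it. One left and one crossed to the waitlist. The total is unchanged, so at least one church had to be found to replace the one that left.

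**Step 2: timing.** Wave 1 participation is already in the past tense in the February 2016 entry, which says Wave 2 recruitment is open. The 6-month form listed in section 16 ("Health Beliefs and Behaviors 6 month amendment") carries the version date 2-2-2016, and the 12-month form 8-2-2016. If those dates approximate first use in Wave 1, its first six months ended around February 2016 and its twelve months around August 2016. A church that first joined in August 2016 could not have started a six-month wait at the Wave 1 baseline. This is inference: no survey date is given for any church.

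**Step 3: the untreated window.** Under the Data collection paragraph of section 4a, Wave 2 is surveyed at baseline 1, baseline 2 (6 months), 12 months and 18 months. The waitlist is therefore untreated only up to baseline 2, while the Aim 1 hypothesis covers 12 months as well.

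**Step 4: effect on precision, for scale only.** Assume 1:1 arms in Wave 1. Wave 1 TIPS versus waitlist goes from 4 v 6 churches to 3 v 8. The church-level variance factor goes from 1/4 + 1/6 = 0.417 to 1/3 + 1/8 = 0.458, a rise of 10%. Power = Φ((p1 − p0)/√v − 1.96), with v = [p1(1 − p1)/m + (k·p1)²]/a + [p0(1 − p0)/m + (k·p0)²]/b for a TIPS and b waitlist churches, using the rates and m above:

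| Assumed k | 4 v 6 | 3 v 8 |
|---|---|---|
| 0.10 | 93% | 90% |
| 0.15 | 80% | 74% |
| 0.20 | 63% | 57% |
| 0.25 | 49% | 43% |

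These rates and cluster sizes belong to the 12-month comparison with standard information, so the table shows only that the precision loss is modest. The main problem is bias, which it does not capture.

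**Step 5: matching.** If pairs were formed within Wave, eight churches make four pairs. Had the two departing churches been partners, three intact pairs would remain. Otherwise two pairs were broken, leaving two intact pairs and two unpartnered churches. The documents do not say which.

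**The case against.** The strongest reply is that little depends on the waitlist. The protocol describes a two-arm trial, and its purpose and hypothesis (section 2) mention no waitlist comparison. The primary analysis is TIPS versus standard information at 12 months. The one SAP sentence that uses the waitlist is worded as exploration. All of this stands, and it limits the importance of the point. It does not cure the hypothesis, which still places the waitlist beside the standard information control.

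Several stronger readings are tempting, but the documents do not support them:

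- *Most of Wave 2 was outside the pool when Waves were assigned.* No assignment date is given. Seventeen (section 4a) or twenty-two (section 8a) churches had supplied support letters, and one attachment of such letters is dated 2013. Listing in an amendment does not date entry to the pool, and one February 2016 entry includes a church marked as existing.
- *All eight waitlist churches selected themselves, or Wave was simply set by availability.* A move for the church's own reasons is documented for one church. Having agreed to take part in Wave 1 does not exclude a prior random assignment.
- *The waitlist lags Wave 1 by six months or more.* Form version dates are not survey dates, and neither form title names a Wave. The August 2016 entry adds one church.
- *The pilot comparison churches' rise from 19% to 41% shows the size of secular drift.* Those churches received standard HIV information, and the rise covers 12 months, against a six-month wait here.
- *The primary comparison is compromised.* Arms are stated to be randomised within Wave, and nothing reported contradicts that.

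**Conclusion.** The point holds for the waitlist contrasts and should be fixed. The stated 8/6 split is contradicted by the protocol's own report of 6/8. Random assignment to Wave does not describe how the final groups were formed, since one church left, one crossed over and further churches were added in 2016. The waitlist is thus not a purely randomised control and is probably not fully concurrent. The first conclusion rests on reported facts. The second rests on amendment and form dates and carries only moderate confidence.

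The documents give no figure from which the bias could be sized. The precision effect is small: a 10% larger church-level variance factor, assuming even arms in Wave 1. The primary TIPS versus standard information comparison keeps its basis, provided arms were randomised within Wave as stated. When arms were assigned, and what became of the partners of the two churches, remain to be reported.

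**What to change.** 1. **Protocol.** Reconcile section 4a with section 8a on the 6/8 split. Report how and when each church received its Wave and its arm, with survey dates by church. Say what happened to the matched partners of the church that left and the church that moved. If Waves were in fact randomised and then departed from, report the departures as such.
2. **SAP Aim 1.** Do not delete the waitlist silently. By a dated, disclosed amendment, state that the waitlist part of the hypothesis is not confirmatory. Label both waitlist contrasts exploratory, not protected by randomisation and possibly non-concurrent, and state that no efficacy claim will be drawn from them.
3. **Pooled model.** Include Wave as a fixed design factor in the TIPS versus standard information model, because arms are randomised within Wave. The SAP's listed terms do not include it.

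The cost is two wording changes, a table of church assignments and one extra model term with 14 churches. The waitlist comparison loses confirmatory standing. The 2017 renewal form says data entry was still under way. If outcome data have been examined since then, the amendment should say so.
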